## **APPENDIX H: Self Geriatric Assessment Measure – Patient Questionnaire**

---

Responsible person name (*Physician, Nurse, or CRA*) \_\_\_\_\_

Assessment Period (as applicable to this study): \_\_\_\_\_

Timepoint 1 (Baseline);  Timepoint 2 (At cycle #4);  Timepoint 3 (End of study)

---

**Patient Instructions:** If you are unable to complete the questionnaire, a member of your health care team will assist you. Please do not have a family member complete the questionnaire for you.

### **A. BACKGROUND INFORMATION**

1. What is the highest grade you finished in school? (*Mark one with an X.*)

 8 th or less	 Vocational/technical school
 9-11 th grade	 Bachelor's degree
 High school graduate/GED	 Advanced degree
 Associate degree/some college	 I prefer not to answer

2. What is your marital status? (*Mark one with an X.*)

 Married	 Separated
 Domestic partnership	 Never married
 Widowed	 I prefer not to answer
 Divorced	

3. With whom do you live? (*Mark all that apply with an X.*)

 Spouse / partner	 Parent(s)/ parent(s)-in-law
 Girlfriend / boyfriend	 Live alone
 Children aged 18 years or younger	 Other specify _____
 Children aged 19 years or older	 Other relative specify _____

---

---

---

4. What is your current employment status? (Mark one with an X.)

 Employed 32 hours or more per week	 Unemployed
 Employed less than 32 hours per week	 Retired
 Homemaker	 Full-time student
 Disabled	 Part-time student
 On medical leave	 Other specify _____

5. How old are you? \_\_\_\_\_ years old

6. What is your race? (Mark one with an X)

 White	 Asian
 Black or African American	 Native Hawaiian or Other Pacific Islander
 Native Indian or Alaskan Native	 Unknown

7. What is your ethnicity? (Mark one with an X)

 Hispanic or Latino
 Non-Hispanic
 Unknown

## B. DAILY ACTIVITIES\*

**PATIENT INSTRUCTIONS:** Indicate your response by marking an X in one box per question.

1. Can you use the telephone...

 without help, including looking up and dialing;
 with some help (can answer phone or dial operator in an emergency, but need a special phone or help in getting the phone number or dialing); or
 are you completely unable to use the telephone?

2. Can you get to places out of walking distance...
  - without help (can travel alone on busses, taxis, or drive your own car);
  - with some help (need someone to help you or go with you when traveling) ; or
  - are you unable to travel unless emergency arrangements are made for a specialized vehicle like an ambulance?
  
3. Can you go shopping for groceries or clothes (assuming you have transportation) ...
  - without help (taking care of all shopping needs yourself, assuming you have transportation);
  - with some help (need someone to go with you on all shopping trips); or
  - are you completely unable to do any shopping?
  
4. Can you prepare your own meals...
  - without help (plan and cook full meals yourself);
  - with some help (can prepare some things but unable to cook full meals yourself) ; or
  - are you completely unable to prepare any meals?
  
5. Can you do your housework...
  - without help (can clean floors, etc);
  - with some help (can do light housework but need help with heavy work); or
  - are you completely unable to do any housework?
  
6. Can you take your own medicines...
  - without help (in the right doses at the right time);
  - with some help (able to take medicine if someone prepares it for you and/or reminds you to take it); or
  - are you completely unable to take your medicines?
  
7. Can you handle your own money...
  - without help (write checks, pay bills, etc.);

- with some help (manage day-to-day buying but need help with managing your checkbook and paying your bills); or
- are you completely unable to handle money?

\* OARS IADL – Fillenbaum, G.G. and Smyer, M.A., 1981

### C. PHYSICAL ACTIVITIES\*

1. The following items are activities you might do during a typical day. Does your health limit you in these activities? (Mark an X in the box on each line that best reflects your situation.)

Activities	Limited a lot	Limited a little	Not limited at all
a. Vigorous activities , such as running, lifting heavy objects, participating in strenuous sports			
b. Moderate activities , such as moving a table, pushing a vacuum cleaner, bowling, or playing golf			
c. Lifting or carrying groceries			
d. Climbing several flights of stairs			
e. Climbing one flight of stairs			
f. Bending, kneeling, or stooping			
g. Walking more than a mile			
h. Walking several blocks			
i. Walking one block			
j. Bathing or dressing yourself			

\* MOS, Physical Functioning Scale – Stewart, A.L. and Ware, J.E., 1992

### D. CURRENT HEALTH RATING\*

Which one of the following phrases best describes you at this time? *(Mark one with an X.)*

- Normal, no complaints, no symptoms of disease

- Able to carry on normal activity, minor symptoms of disease
- Normal activity with effort, some symptoms of disease
- Care for self, unable to carry on normal activity or do active work
- Require occasional assistance but able to care for most of personal needs
- Require considerable assistance for personal care
- Disabled, require special care and assistance
- Severely disabled, require continuous nursing care

\* Patient KPS – Loprinzi, C.L., et al., 1994

---

#### **E. FALLS**

How many times have you fallen in the last 6 months? \_\_\_

---

#### **F. YOUR MEDICATIONS**

Are you taking medications?

Yes       No

How many prescribed medications are you taking? \_\_\_ medications

How many over-the-counter medications are you taking? \_\_\_ medications

How many herbs and vitamins are you taking? \_\_\_ herbs and vitamins

---

#### **G. YOUR HEALTH**

##### **1. Your General Health\***

**Patient Instructions:** Do you have any of the following illnesses at the present time, and if so, how much does it interfere with your activities: **Not at All, A Little or A Great Deal?** (Mark an X in the box that best reflects your answer.)

**If you have this illness:**

**How much does it interfere with your activities?**

Illness	No	Yes	Not at all	A little	A great deal
a. Other cancers or leukemia		 →			
b. Arthritis or rheumatism		 →			
c. Glaucoma		 →			
d. Emphysema or chronic bronchitis		 →			
e. High blood pressure		 →			
f. Heart trouble		 →			
g. Circulation trouble in arms or legs		 →			
h. Diabetes		 →			
i. Stomach or intestinal disorders		 →			
j. Osteoporosis		 →			
k. Liver disease		 →			
l. Kidney disease		 →			
m. Stroke		 →			
n. Depression		 →			

\* OARS IADL – Fillenbaum, G.G. and Smyer, M.A., 1981

2. How is your eyesight (with glasses or contacts)? (Mark one with an X.)

- Excellent
- Good
- Fair
- Poor

Totally blind

3. How is your hearing (with a hearing aid, if needed)? (Mark one with an X.)

Excellent

Good

Fair

Poor

Totally deaf

4. Do you have any other physical problems or illnesses (other than listed in questions 1-4) at the present time that seriously affect your health?

No

Yes (If yes), specify \_\_\_\_\_

(If yes), how much does this interfere with your activities? (Mark one with an X.)

Not at all       Somewhat       A great deal

\* OARS IADL – Fillenbaum, G.G. and Smyer, M.A., 1981

## H. NUTRITIONAL STATUS

1. Have you lost weight involuntarily over the past 6 months?

No

Yes

If yes, how much?

\_\_\_\_\_ pounds

2. What is your weight now?

\_\_\_\_\_ pounds

3. What was your weight 6 months ago?

\_\_\_\_\_ pounds

## I. HEALTH QUESTIONNAIRE\*

**INSTRUCTIONS: These questions are about how you have been feeling within the past month. Please mark an "X" in the box on each line that best reflects your situation.**

How much of the time during the past month:	All of the Time	Most of the Time	A Good Bit of the Time	Some of the Time	A Little of the Time	None of the Time
1. has your daily life been full of things that were interesting to you?						
2. did you feel depressed?						
3. have you felt loved and wanted?						
4. have you been a very nervous person?						
5. have you been in firm control of your behavior, thoughts, emotions, feelings?						
6. have you felt tense or high-strung?						
7. have you felt calm and peaceful?						
8. have you felt emotionally stable?						
9. have you felt downhearted and blue?						
10. have you felt restless, fidgety, or impatient?						
11. have you been moody, or brooded about things?						
12. have you felt cheerful, light-hearted?						
13. have you been in low or very low spirits?						
14. were you a happy person?						
15. did you feel you had nothing to look forward to?						

16. have you felt so down in the dumps  
that nothing could cheer you up?

17. have you been anxious or worried?

\* MHI-17 – Stewart, A.L. and Ware, J.E., 1992

## **J. SOCIAL ACTIVITIES\***

1. During the past 4 weeks, how much time has your physical health or emotional problems interfered with your social activities (like visiting with friends, relatives, etc.)?  
*(Mark one with an X.)*

- All of the time
- Most of the time
- Some of the time
- A little of the time
- None of the time

2. Compared to your usual level of social activity, has your social activity during the past 6 months decreased, stayed the same, or increased because of a change in your physical or emotional condition? *(Mark one with an X.)*

- Much less socially active than before
- Somewhat less socially active than before
- About as socially active as before
- Somewhat more socially active as before
- Much more socially active than before

3. Compared to others your age, are your social activities more or less limited because of your physical health or emotional problems? *(Mark one with an X.)*

-----

- Much more limited than others
- Somewhat more limited than others
- About the same as others
- Somewhat less limited than others
- Much less limited than others

\* MOS, Social Activities – Stewart, A.L. and Ware, J.E., 1992

## K. SOCIAL SUPPORT\*

**INSTRUCTIONS: People sometimes look to others for companionship, assistance or other types of support. How often is each of the following kinds of support available to you if you need it? (Mark an X in the box on each line that best reflects your situation.)**

	None of the Time	A Little of the Time	Some of the Time	Most of the Time	All of the Time
1. Someone to help you if you were confined to bed.					
2. Someone you can count on to listen to you when you need to talk.					
3. Someone to give you good advice about a crisis.					
4. Someone to take you to the doctor if you needed it.					
5. Someone to give you information to help you understand a situation.					
6. Someone to confide in or talk to about yourself or your problem.					
7. Someone to prepare your meals if you were unable to do it yourself.					
8. Someone whose advice you really want.					
9. Someone to help you with daily chores if you were sick.					
10. Someone to share your most private worries					

---

and fears with.

---

11. Someone to turn to for suggestions about how to deal with a personal problem.

12. Someone who understands your problems.

---

\* MOS Social Support Survey – Sherbourne, C.D. and Stewart, A.L., 1991

## L. SPIRITUALITY/RELIGION\*

**Directions: Please answer the following questions about your religious beliefs and/or involvement. (Please mark an “X” in the box on each line that best reflects your situation.)**

1. How often do you attend church, synagogue, or other religious meetings? *(Mark one with an X.)*  
 More than once per week  
 Once a week  
 A few times a month  
 A few times a year  
 Once a year or less  
 Never
  
2. How often do you spend time in private religious activities, such as prayer, meditation or Bible study? *(Mark one with an X.)*  
 More than once a day  
 Daily  
 Two or more times per week  
 Once a week  
 A few times a month  
 Rarely or never

*The following section contains 3 statements about religious belief or experience. Please mark the extent to which each statement is true or not true for you.*

3. In my life, I experience the presence of the Divine (i.e., God). *(Mark one with an X.)*

- Definitely true of me
- Tends to be true
- Unsure
- Tends *not* to be true
- Definitely *not* true

4. My religious beliefs are what really lie behind my whole approach to life. *(Mark one with an X.)*

- Definitely true of me
- Tends to be true
- Unsure
- Tends *not* to be true
- Definitely *not* true

5. I tried hard to carry my religion over into all other dealings in my life. *(Mark one with an X.)*

- Definitely true of me
- Tends to be true
- Unsure
- Tends *not* to be true
- Definitely *not* true

\* DUREL: Duke University Religion Index – Koenig et al., 1997

## **M. YOUR FEELINGS\***

1. Do you often feel sad or depressed? *(Mark one with an X.)*

- No
- Yes

2. How would you describe your level of anxiety, on the average? Please circle the number (0-10) best reflecting your response to the following that describes your feelings **during the past week, including today**.

0	1	2	3	4	5	6	7	8	9	10
No anxiety can be						Anxiety as bad as it				

\* Mahoney et al., 1994; LASA – Locke et al., 2007

---

#### **N. FACT-B**

Below is a list of statements that other people with your illness have said are important. Please circle or mark one number per line to indicate your response as it applies to the past 7 days.

	PHYSICAL WELL-BEING	Not at all	A little bit	Some- what	Quite a bit	Very much
GP1	I have a lack of energy .....	0	1	2	3	4
GP2	I have nausea .....	0	1	2	3	4
GP3	Because of my physical condition, I have trouble meeting the needs of my family .....	0	1	2	3	4

GP4	I have pain	0	1	2	3	4
GP5	I am bothered by side effects of treatment	0	1	2	3	4
GP6	I feel ill	0	1	2	3	4
GP7	I am forced to spend time in	0	1	2	3	4
SOCIAL/FAMILY WELL-BEING		Not at all	A little bit	Some-what	Quite a bit	Very much
GS1	I feel close to my friends	0	1	2	3	4
GS2	I get emotional support from my family	0	1	2	3	4
GS3	I get support from my friends	0	1	2	3	4
GS4	My family has accepted my illness	0	1	2	3	4
GS5	I am satisfied with family communication about my	0	1	2	3	4

	illness	.....					
GS6	I feel close to my partner (or the person who is my main support)	.....	0	1	2	3	4
Q1	Regardless of your current level of sexual activity, please answer the following question. If you prefer not to						
GS7	I am satisfied with my sex life	.....	0	1	2	3	4

Please circle or mark one number per line to indicate your response as it applies to the past 7 days.

	EMOTIONAL WELL-BEING		Not at all	A little bit	Some-what	Quite a bit	Very much
GE1	I feel sad	.....	0	1	2	3	4
GE2	I am satisfied with how I am coping with my illness	.....	0	1	2	3	4
GE3	I am losing hope in the fight against my illness	.....	0	1	2	3	4

	GE4	I feel nervous	0	1	2	3	4
	GE5	I worry about dying	0	1	2	3	4
	GE6	I worry that my condition will get	0	1	2	3	4
	FUNCTIONAL WELL-BEING	Not at all	A little bit	Some-what	Quite a bit	Very much	
	GF1	I am able to work (include work at home)	0	1	2	3	4
	GF2	My work (include work at home) is fulfilling	0	1	2	3	4
	GF3	I am able to enjoy life	0	1	2	3	4
	GF4	I have accepted my illness	0	1	2	3	4
	GF5	I am sleeping well	0	1	2	3	4
	GF6	I am enjoying the things I usually do for fun	0	1	2	3	4

GF7

I am content with the quality of my life      0      1      2      3      4

Please circle or mark one number per line to indicate your response as it applies to the past 7 days.

	ADDITIONAL CONCERNS	Not at all	A little bit	Some-what	Quite a bit	Very much
B1	I have been short of breath .....	0	1	2	3	4
B2	I am self-conscious about the way I dress .....	0	1	2	3	4
B3	One or both of my arms are swollen or tender .....	0	1	2	3	4
B4	I feel sexually attractive .....	0	1	2	3	4
B5	I am bothered by hair loss .....	0	1	2	3	4
B6	I worry that other members of my family might someday get the same illness I have .....	0	1	2	3	4
B7	I worry about the effect of stress on my illness .....	0	1	2	3	4

B8	I am bothered by a change in weight .....	0	1	2	3	4
B9	I am able to feel like a	0	1	2	3	4
P2	I have certain parts of my body where I experience pain .....	0	1	2	3	4

## O. QUESTIONS CONCERNING THE QUESTIONNAIRE

1. Were there any questions difficult to understand?  No  Yes

*(If yes), which questions were they?*

2. Was the time it took to answer all the questions too long, just right or too short?

Too short → How long would you have liked the questionnaire to be? \_\_\_\_ minutes

Just right

Too long → How long would you have liked the questionnaire to be? \_\_\_\_ minutes

Which items would you remove?

3. Did you find any of the questions upsetting?  No  Yes

*(If yes), which questions were they?*

Could you tell me why they were upsetting?

4. Do you think the questionnaire left out any questions that were important to ask?

**Thank you for your participation.**

## **APPENDIX I: Geriatric Assessment Healthcare Professional Questionnaire**

**I. This form completed by: (Mark all that apply with an X.) Assessment Period (as applicable to this study)**

Physician       Nurse       CRA       Pre-treatment     Cycle #4     End of Treatment

**Mark box with an “X”, if form was not completed at specified timepoint and specify reason:**

*(Mark one with an X.)*       Patient refused       Patient withdrew consent       Not done

Other, specify \_\_\_\_\_

## II. Karnofsky Performance Status: %

Please rate your assessment of patient's Karnofsky Performance Status as of date this form is completed. *(Scale is listed below.)*

DEFINITION	%	CRITERIA
Able to carry on normal activity and able to work. No special care is needed.	100	Normal: no complaints; no evidence of disease
	90	Able to carry on normal activity; minor signs or symptoms of disease.
	80	Normal Activity with effort; some signs or symptoms of disease.
Unable to work. Able to live at home, and for most personal needs. A varying amount of assistance is needed	70	Cares for self. Unable to carry on normal activity or to do active work.
	60	Requires occasional assistance, but is able to care for most of his needs
	50	Requires considerable assistance and frequent medical care
Unable to care for self. Requires equivalent of institutional or hospital care. Disease may be progressing rapidly	40	Disabled; requires special care and assistance
	30	Severely disabled; hospitalization is indicated although death not imminent.
	20	Very sick; hospitalization necessary; active supportive treatment necessary.
	10	Moribund; fatal processes progressing rapidly
	0	Dead.

\* Physician KPS – Karnofsky, D.A. and Burchenal, J.H., 1949

Geriatric Assessment Healthcare Professional Questionnaire

### **III. Timed “Up and Go”\***

**INSTRUCTIONS:** The timed “Up and Go” measures, in seconds, the time it takes for an individual to stand up from a standard arm chair (approximate seat height of 46 cm [approximately 1.5 ft]), walk a distance of 3 meters (approximately 10 feet), turn, walk back to the chair, and sit down again. The subject wears his/her regular footwear and uses their customary walking aid (none, cane, walker, etc.) No physical assistance is given.

The subject starts with his back against the chair, his arm resting on the chair's arm, and his walking aid in hand. He is instructed that on the word "go", he is to get up and walk at a comfortable and safe pace to a line on the floor three meters (approximately ten feet) away, turn, and return to the chair and sit down again. The subject walks through the test once before being timed in order to become familiar with the test. Either a wrist watch with a second hand or a stop-watch can be used to time the performance.

**Time to perform "Up and Go" seconds :** \_\_\_\_\_

#### **IV. COGNITION : Orientation-Memory-Concentration Test**

Errors	Patient's Final Score	Maximum Response Weight	Score
1. What year is it now?  x	□□□□ 4	1 =	□□
[without looking at a calendar]			
2. What month is it now?  x	□□ 3	1 =	□□
[without looking at a calendar]			

#### **Memory Phrase**

Repeat this phrase after me: 'John Brown, 42 Market Street, Chicago'.

3. About what time is it  x	□□:□□ 3	1 =	□□
[within 1 hour – without looking at your watch]			
4. Count backwards from  20 to 1.	2 x	2 =	□□

5. Say the months in reverse 2  
x      2 =

order.

6. Repeat the memory phrase 5  
x 2 =

Digitized by [contact]

### Score:

### Total

**Scoring:** For items 1 to 3, the response is either correct (score 0) or incorrect (score 1). For items 4 to 6, subtract one point for each error (item 4 and 5 maximum error is 2; for item 6, maximum error is 5); total all scores in “Final Score” column. **Total score of 11 or greater indicates cognitive impairment; please notify MD and assist patient in completing questionnaires.** Maximum score = 28

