#### 7.6.4.1 Additional Studies

##### **Geriatric assessment(GA):**

The comprehensive geriatric assessment questionnaires are listed in **Appendix H (Self Geriatric Assessment Measure – Patient Questionnaire)** and **Appendix I (Healthcare Professional Questionnaire)**. As part of the study initiation, the study team (including PI, nurses, and CRAs) will be trained on the use of geriatric assessment questionnaires as well as potential interventions based on the results. The GA results will be made available to treating physicians and nurse. The individual treating physician will follow up on the GA results using their best clinical judgment. Furthermore, if a patient scores 11 or greater (a potential indicator of cognitive impairment) on the Blessed Orientation Memory and Concentration Test, the results will be reported to the treating physician so that further work-up and treatment can be performed as they deemed medically appropriate. Furthermore, if the patient endorses depression or anxiety (score greater than or equal to 5), the doctor will be notified.

If patient's native language was not covered by the current language forms, Geriatric assessment form can be omitted with clear documentation.

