**VII. Scoring**

- a) Did the patient score  $\geq 11$  on the Blessed Orientation-Memory-Concentration Test (see previous page)?

- No
- Yes (if yes, notify the patient's treating physician)

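### Appendix I, section IV: the cognition test adds points for errors on items 1 to 3 but subtracts them on items 4 to 6, which contradicts its own higher-is-worse cut-off

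*Combined protocol and SAP*

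**What the plan says.** Appendix I, section IV sets out six items, each with a maximum number of errors and a weight, and a scoring note beneath them.

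- First three items: "For items 1 to 3, the response is either correct (score 0) or incorrect (score 1". Errors raise the score.
- Last three items: "For items 4 to 6, subtract one point for each error". The limits are "item 4 and 5 maximum error is 2; for item 6, maximum error is 5". The note does not say what the points are subtracted from.
- Reading the total: "Total score of 11 or greater indicates cognitive impairment; please notify MD and assist patient in completing questionnaires". The stated maximum is 28.

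The same threshold appears in two other places. Section 7.6.4.1 (Geriatric assessment) has the result reported to the treating physician "if a patient scores 11 or greater (a potential indicator of cognitive impairment"). Appendix I, section VII asks whether the score reached 11 and answers with "Yes (if yes, notify the patient's treating physician").

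Cognition is one of the geriatric assessment domains listed in the synopsis. Section 2.2 makes the assessment's role in predicting toxicity a secondary objective, and Section 15.3 plans generalized linear models to explore factors from it.

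**The concern.** One total combines items on which errors add with items on which errors are to be taken away, and that total is then read with higher meaning worse. A rater who follows the sentence for items 4 to 6 moves the score away from the impairment threshold with each mistake the patient makes.

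Two uses are exposed. The total decides whether the physician is alerted and whether staff help the patient with the questionnaires. It is also the cognition measure in the geriatric assessment. If raters resolve the sentence differently, the recorded totals are not on one scale, and in a study of 40 patients a few forms scored the other way could distort that predictor.

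**Working it through.** **Inputs** (Appendix I, section IV). The column layout is broken in the available text, but each item's product of maximum errors and weight can still be read.

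| Item | Max errors × weight | Points |
|---|---|---|
| 1 Year | 1 × 4 | 4 |
| 2 Month | 1 × 3 | 3 |
| 3 Time | 1 × 3 | 3 |
| 4 Counting backwards | 2 × 2 | 4 |
| 5 Months in reverse | 2 × 2 | 4 |
| 6 Memory phrase | 5 × 2 | 10 |

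Items 1 to 3 carry 4 + 3 + 3 = 10 points. Items 4 to 6 carry 4 + 4 + 10 = 18 points, and 18/28 = 64%.

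**The plan's own figure.** With errors added, total = sum of (errors × weight). Its maximum is 10 + 18 = 28, which reproduces the stated maximum. No errors gives 0, all errors gives 28, and 11 lies inside the range with higher meaning worse.

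**Subtracting from zero, weighted.** Total = (weighted errors on items 1 to 3) − (weighted errors on items 4 to 6).
- Highest: 10 − 0 = 10
- Lowest: 0 − 18 = −18
- Every item failed: 10 − 18 = −8

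The ceiling of 10 is below 11. Leaving out all weights gives a range of −9 to +3. Weighting only items 1 to 3 gives −9 to +10. Neither reaches 11.

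**Subtracting from weighted full marks.** This needs a starting value of 4 + 4 + 10 = 18 for items 4 to 6, which the form does not state.
- No errors: 0 + 18 = 18, flagged
- Every item failed: 10 + 0 = 10, not flagged
- Highest: items 1 to 3 wrong, items 4 to 6 error-free, 10 + 18 = 28

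**Subtracting from unweighted full marks.** The start is 2 + 2 + 5 = 9, also not stated. No errors gives 9, every item failed gives 10, and neither is flagged. The highest total is 10 + 9 = 19.

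**All possible error patterns.** There are 2 × 2 × 2 × 3 × 3 × 6 = 432.

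| Reading | Range | Patterns at 11 or more |
|---|---|---|
| Errors added, weighted | 0 to 28 | 323 |
| Subtract from zero, weighted | −18 to 10 | 0 |
| Subtract from weighted full marks | 0 to 28 | 323 |
| Subtract from unweighted full marks | 0 to 19 | 170 |

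The first and third readings flag the same number of patterns but agree on the flag in only 250 of 432. These are counts of patterns, not expected proportions of patients.

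**The case against.** The strongest reply is that the form supplies its own working rule. It has columns for maximum errors and weight, the first three items set the direction, and the threshold says that high is bad. Together these point to errors times weight, summed. That stands. It makes this a wording slip, not a flawed instrument, and nothing in the documents shows that any form was mis-scored.

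Section 7.6.4.1 also softens the consequence. Study staff are to be trained on the questionnaires, and the results go to treating physicians and nurses whatever the score. The alert at 11 is therefore not the only route by which impairment could be noticed. The training text gives no scoring rule that would override the form, however, so the contradiction remains.

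Four stronger readings are tempting and are not supported.

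- *The maximum of 28 proves that errors must add.* It does not. Subtracting from weighted full marks also peaks at 28. That reading fails because it runs the wrong way against the cut-off.
- *The form flags patients who make no errors.* That needs the unstated start of 18. From an unweighted start of 9, such a patient scores 9 and is not flagged.
- *Impaired patients have been hidden.* That would require evidence of how raters scored, which the documents do not contain.
- *Section VII is deficient because it checks only cognition.* Section 7.6.4.1 itself carries the other duty: "if the patient endorses depression or anxiety (score greater than or equal to 5), the doctor will be notified". Nothing requires that duty to be repeated as a box in Appendix I. The sentence names no items, and Appendix H asks about depression and anxiety in both sections I and M.

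**Conclusion.** The scoring rule is wrong as written. The sentence for items 4 to 6 conflicts with the direction of items 1 to 3 and with the cut-off, and it governs 18 of the 28 weighted points. Subtracting from zero caps the weighted total at 10, so the notification in Section 7.6.4.1 and Appendix I, sections IV and VII could not trigger. Other outcomes depend on a starting value that a rater would have to supply.

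The fault is confined to one word. The cut-off of 11 and the maximum of 28 are coherent once errors are added. The effect is on the notification trigger and on the cognition part of the geriatric assessment, a secondary and exploratory input. The primary endpoint, the sample size and the diarrhea monitoring boundary do not use this score.

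The conclusion rests on the maximum errors and weights as read from a form whose layout is broken in the text; the item products do not depend on the column order. How raters scored in practice is unknown.

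**What to change.** In the Appendix I, section IV scoring note, replace the instruction to subtract with: *for items 4 to 6, score one point for each error, up to the stated maximum; multiply each item score by its weight and sum.* Add: *range 0 to 28, higher is worse.* Leave the threshold and the maximum as they are, and cover the corrected rule in the geriatric assessment training.

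Check completed forms and re-score from the recorded item errors where needed. A bare entry on items 4 to 6 may be ambiguous: a 2 on item 4 could mean two errors, or full marks with none lost. Establish which convention the rater used before re-scoring, and mark the total as unresolved if that cannot be done.

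The cost is one sentence on one form and a review of existing forms. No patient needs a new assessment.
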